5.1.3 Second Period

Subjects who complete the First Period will have a visit every 4 weeks \pm 7 days relative to Visit 3 for the first 6 months of administration and then every 12 weeks \pm 14 days thereafter. Subjects will continue to receive LEV 14 to 42mg/kg/day in subjects aged 1 month to <6 months or LEV 20 to 60mg/kg/day for subjects aged \geq 6 months <4 years at the discretion of the Investigator.

When subjects aged <6 months at the time of study enrollment reach 6 months of age, they can take a maximum of LEV 60mg/kg/day.

A final visit will be required 2 weeks \pm 7 days after the final dose of LEV, or sooner if the subject will continue LEV (prescribed by the primary care provider as commercial LEV) after study completion.

5.1.4 Study duration per subject

The study duration is as follows:

Retrospective Baseline Period

Seizure counts during the 2 weeks prior to Visit 1 will be used as a Retrospective Baseline Period.

First Period

- Selection Period (maximum of 9 days)
- Evaluation Period (6 weeks)
- Down-Titration Period (up to 4 weeks)

- Safety Follow-Up Period (2 weeks)

Second Period

- Maintenance Period (until approval or the program is discontinued)
- Down-Titration Period (up to 4 weeks)
- Safety Follow-Up Period (2 weeks)

The end of the study is defined as the date of the final visit of the final subject in the study.

5.1.5 Planned number of subjects and sites

The planned number of evaluable subjects in the First Period will be a total of 38 subjects for the primary efficacy analysis. Subjects will be enrolled into 4 age groups (1 month to <6 months, 6 months to <1 year, 1 year to <2 years, and 2 years to <4 years), with a minimum of 5 subjects in each age group.

The planned number of monotherapy subjects will be a total of 10 subjects.

It is planned to have those subjects recruited in approximately 20 sites.

5.1.6 Anticipated regions and countries

The study will be conducted in Japan.

5.2 Schedule of study assessments

For Visit 4 through Visit 6, planned clinic visits should be scheduled as indicated with a window of ± 4 days relative to Visit 3. For Visit 8 through Visit 15, planned clinic visits should be scheduled as indicated with a window of ± 7 days relative to Visit 3. From Visit 16 onward, planned clinic visits should be scheduled as indicated with a window of ± 14 days relative to Visit 3.

Table 5–1: Schedule of assessments

Visit Study Week	First Period						Second Period											
	Selection Period		Evaluation Period ^a				Maintenance Period ^b											
	V1	V2	V3	V4	V5	V6	V7	V8	V9	V10	V11	V12	V13	V14	V15	V16 ^c ...	V17 ^d ...	
	D-9 to D-2	D-2 to D0	W0	W2	W4	W6	W8	W10	W12	W14	W18	W22	W26	W32	W38	W50...	W62...	
Written informed consent	X																	
Inpatient				X		X												
Registration	X		X															
Eligibility assessment	X		X															
Medical/procedures history	X																	
Demographics	X																	
AED history	X																	
Epilepsy history	X																	
Physical examination	X																	
Neurological examination	X																	
Vital signs ^e	X		X	X	X	X	X			X	X	X	X		X	X	X	
Seizure counts ^f	X		X	X	X	X	X			X	X	X	X		X	X	X	
Laboratory safety assessment ^h	X			X	X	X				X			X		X	X	X	
LEV plasma level			X	X	X	X	X			X	X	X	X					
Body weight	X		X	X	X	X	X			X	X	X	X		X	X	X	
Height	X												X		X			
Concomitant AED(s)	X		X ^g	X	X	X	X			X	X	X	X		X	X	X	
Concomitant non-AED(s)	X		X ^g	X	X	X	X			X	X	X	X		X	X	X	

Table 5–1: Schedule of assessments

Visit Study Week	First Period						Second Period											
	Selection Period		Evaluation Period ^a				Maintenance Period ^b											
	V1	V2	V3	V4	V5	V6	V7	V8	V9	V10	V11	V12	V13	V14	V15	V16 ^c ...	V17 ^d ...	
	D-9 to D-2	D-2 to D0	W0	W2	W4	W6	W8	W10	W12	W14	W18	W22	W26	W32	W38	W50...	W62...	
Concomitant medical procedures	X		X ^g	X	X	X			X		X	X	X			X	X	X
Adverse events	X		X ^g	X	X	X			X		X	X	X			X	X	X
Dispense/return study drug			X ⁱ	X	X	X			X		X	X	X			X	X	X
Study drug compliance				X	X	X			X		X	X	X			X	X	X
ECG	X																X	
CT scan/MRI ^j	X																	
EEG ^k	X																	
IVRS/IWRS	X		X	X	X	X			X		X	X	X			X	X	X
Dispense/collect DRC	X ^l		X	X	X	X			X		X	X	X			X	X	X
Dispense subject's ID card	X																	
Fallback option ^m				X	X													
C-SSRS ⁿ																X ⁿ	X ⁿ	

AED=antiepileptic drug; C-SSRS=Columbia-Suicide Rating Scale; CT=computed tomography; D=day; DRC=daily record card; ECG=electrocardiogram; EDV=Early Discontinuation Visit; EEG=electroencephalogram; ID=identification; IVRS=interactive voice response system; IWRS=interactive web response system; LEV=levetiracetam; MRI=magnetic resonance imaging; SFU=Safety Follow-Up; V=visit; W=week

Note: See [Table 5–3](#) for the schedule of assessments for the Down-Titration and SFU Periods.

^a After beginning the study medication, subjects who withdraw prematurely must have W6 evaluations and the EDV evaluations.

^b In the Maintenance Period, visits will occur every 4 weeks from V8 to V13, and every 12 weeks thereafter.

^c Even numbered visits.

^d Odd numbered visits.

^e Including temperature, blood pressure, and heart rate.

^f At V1, collect seizure count for seizures that occurred in the prior 2 weeks.

Table 5–1: Schedule of assessments

Visit Study Week	First Period						Second Period											
	Selection Period		Evaluation Period ^a				Maintenance Period ^b											
	V1	V2	V3	V4	V5	V6	V7	V8	V9	V10	V11	V12	V13	V14	V15	V16 ^c ...	V17 ^d ...	
	D-9 to D-2	D-2 to D0	W0	W2	W4	W6	W8	W10	W12	W14	W18	W22	W26	W32	W38	W50...	W62...	

^g Recorded from end of V1 through V3.

^h If clinically significant laboratory abnormalities are present at V1, repeat samples must be obtained for blood chemistry and hematology. The results should be available prior to V3, and UCB or its designee should be contacted regarding clinically significant abnormalities.

ⁱ Dispense study drug at V3.

^j Only for subjects who have not had a CT scan or MRI confirming the absence of a progressive lesion since being diagnosed with epilepsy, or have changes on physical examination which would suggest a lesion has occurred since the last imaging procedure.

^k If the EEG exam was not performed prior to V1, the assessment needs to be completed, and results must be available prior to V3.

^l Dispense DRC.

^m Fallback option is permitted. See Section 5.1.2 for details.

ⁿ C-SSRS to be performed at each visit for subjects aged ≥ 6 years.

Table 5–2: Schedule of assessments for subjects who are 48h video-EEG failures

Not applicable.

This document cannot be used to support any marketing application and any extensions or variations thereof.
PUBLIC COPY

Table 5–3: Schedule of assessments for Down-Titration and SFU Periods

Visit Study Week	EDV ^a			SFU ^b
	W0	W2	W4	
Vital signs ^c	X	X	X	X
Seizure counts	X	X	X	X
Laboratory safety assessments	X			X
Body weight	X	X	X	X
Height	X			X
Concomitant AED(s)	X	X	X	X
Concomitant non-AED(s)	X	X	X	X
Concomitant medical procedures	X	X	X	X
Adverse events	X	X	X	X
Dispense/return study drug	X	X	X	
Study drug compliance	X	X	X	
ECG	X			X ^d
IVRS/IWRS	X	X	X	X
Dispense/collect DRC	X	X	X	X ^e
C-SSRS ^f	X ^f	X ^f	X ^f	X ^f

AED=antiepileptic drug; C-SSRS=Columbia-Suicide Severity Rating Scale; CT=computed tomography; D=day; DRC=daily record card; ECG=electrocardiogram; EDV=Early Discontinuation Visit; ID=identification; IVRS=interactive voice response system; IWRS=interactive web response system; LEV=levetiracetam; MRI=magnetic resonance imaging; SFU=Safety Follow-Up; V=visit; W=week

^a The dose will be decreased by LEV 14mg/kg/day for subjects aged 1 month to <6 months or by LEV 20mg/kg/day for subjects aged 6 months to <4 years at 2-week intervals to 0mg/kg/day.

^b Two weeks after final dose of study drug.

^c Including temperature, blood pressure, and heart rate.

[figure not shown]
^d Performed only if abnormal at EDV.

^e Collect DRC.

^f C-SSRS to be performed at each visit for subjects aged ≥ 6 years.

5.3 Schematic diagram

Figure 5–1: Schematic for subjects in the First and Second Periods

6m admin=6 months of administration; DRC=daily record card; V=Visit; W=weeks

Note: The value in parentheses for dose is for subjects 1 month to <6 months of age.

5.4 Rationale for study design and selection of dose

Levetiracetam has been developed as adjunctive therapy in the treatment of partial seizures in children aged 1 month to <4 years with epilepsy. The EMA and FDA have approved the new indication as adjunctive treatment in children down to 1 month of age with partial seizures in Sep 2009 and Dec 2011, respectively. The approved dosage and administration for infants aged 1 month to < 6 months is 14 to 42 mg/kg/day, and for young children aged 6 months to <4 years, the approved dose is 20 to 60 mg/kg/day. These dose ranges were determined based on the results of N01288, a population PK analysis. The results show that the recommended dose ranges are 14 to 42mg/kg/day for infants aged <6 months, approximately 70% of the dose for 4-year-olds (20 to 60mg/kg/day, demonstrating equivalent exposure to 1000 to 3000mg/kg/day in adults) and 20 to 60mg/kg/day for children aged 6 months or older (the same dose range as for 4-year-olds). At the PMDA consultation, they suggested that the final dosage and administration (including up-titration method) should be established based on a confirmatory study. Based on this suggestion, EP0100 is planned to evaluate the efficacy of LEV at the same dosage approved by FDA and EMA, and the dose will be increased at 2-week intervals during the 6-week Evaluation Period.

6 SELECTION AND WITHDRAWAL OF SUBJECTS

Subjects who complete the First Period can start the Second Period without re-confirmation of the inclusion/exclusion criteria.

6.1 Inclusion criteria

To be eligible to participate in this study, all of the following criteria must be met:

- 1a. An Institutional Review Board (IRB)/Independent Ethics Committee (IEC) approved written Informed Consent form is signed and dated by the parent(s) or legal representative. Subject/legal representative/caregiver is considered reliable and capable of adhering to the protocol (eg, able to understand and complete diaries), visit schedule, or medication intake according to the judgment of the Investigator.
- 2a. Subject must have a diagnosis of epilepsy with partial onset seizures (ie, seizures of focal onset), whether or not secondarily generalized.
Subject has had an EEG and a brain computerized tomography (CT) scan or brain magnetic imaging (MRI) consistent with a diagnosis of localized epilepsy according to the International Classification of Epilepsies and Epileptic Syndromes (1989) (see Section 17.2) and consistent with partial onset seizures according to the Classification of Epileptic Seizures (1981) (see Section 17.1). If the EEG and brain CT scan and brain MRI were not performed prior to the Screening Visit (Visit 1), the assessment needs to be completed and results must be available prior to Visit 3.
3. Subject must be male or female from 1 month to <4 years of age. Pre-term infants aged <1 year are to be stratified into an appropriate age category using the best estimate of their corrected gestational age.
4. For subjects on adjunctive therapy, subject must be on a stable AED regimen (ie, a maximum of 2 AEDs) for the Selection and Evaluation Periods of the study. Minor adjustments to the

dose of current AEDs are allowed only prior to Visit 1. Monotherapy subjects must not receive AED treatment, receive temporary AED treatment, or switch an AED prior to Visit 1.

5. Subject weighs $\geq 3.0\text{kg}$.
6. Subject may have Vagal Nerve Stimulation (VNS) which has been implanted for at least 6 months prior to Visit 1; the settings must be stable for at least 2 months prior to Visit 1. Activated VNS must be counted as 1 of the 2 AEDs.
- 7a. Subject must have experienced at least 2 observable partial seizures (ie, seizures of focal onset as determined by EEG), with or without secondary generalization during each 7-day period during the 2 weeks prior to Visit 1. This time period (the 2 weeks prior to Visit 1) will be referred to as the Retrospective Baseline Period. This seizure information (including type, frequency, and date) must have been recorded on a daily record card (DRC) in order to be acceptable.
8. Deleted.
9. Deleted.
10. If epilepsy surgery has been performed prior to study entry, subjects must have a documented failed epilepsy surgery outcome at least 4 weeks prior to Visit 1.
11. The use of intermittent benzodiazepines, phenobarbitals, and phenytoins is allowed as long as the frequency is not greater than 1 single administration per week for at least 2 weeks prior to Visit 1 and throughout study participation. If benzodiazepines are used more than once a week, they must be considered as 1 of the AEDs.

6.2 Exclusion criteria

Subjects are not permitted to enroll in the study if any of the following criteria is met:

1. Subject has been taking any medication (other than their concomitant AEDs) that influences the central nervous system (CNS) for which they had not been on a stable regimen for at least 1 month prior to Visit 1.
2. Subject is taking any medication that may interfere with the absorption, distribution, metabolism, or excretion of the concomitant AEDs or LEV during the course of the study.
3. Subject has received any investigational medication or device within 30 days prior to Visit 1.
4. Subject has taken LEV prior to the study.
5. Subjects using felbamate who have presented with clinically significant abnormalities for WBCs, RBCs, platelets, and/or hepatic function during felbamate treatment, and subjects who are taking felbamate <1 year from the date of Visit 1.
6. Subject has a history of status epilepticus requiring hospitalization during the 30 days prior to Visit 1, except for status epilepticus occurring during the first 10 days of life.
7. Subject has a treatable seizure etiology (ie, febrile seizures).
8. Subject is on a ketogenic diet (concomitantly or within 30 days prior to Visit 1).
9. Subject has epilepsy secondary to progressing cerebral diseases.

10. Subject has a current diagnosis of Rasmussen's syndrome, Landau-Kleffner disease or Lennox-Gastaut syndrome.
11. Subject has clinically significant deviations from reference range values for renal function or any of the other laboratory parameters required for this study, as determined by the Investigator.
12. Subject has any clinically significant acute or chronic illness (as determined during the physical examination or from other information available to the Investigator).
13. Subject has an allergy to pyrrolidine derivatives or a history of multiple drug allergies.
14. Subject is known to have a terminal illness.
15. Subject has a disorder or condition that may interfere with the absorption, distribution, metabolism, or excretion of medications.
16. Subject has a history of or presence of pseudoseizures.
17. Subject has any medical condition that might interfere with the subject's study participation (ie, serious infection, scheduled elective surgery, severe scalp eczema, etc.).
18. Subject has ≥ 3 times the upper limit of normal (ULN) of any of the following: alanine aminotransferase (ALT), aspartate aminotransferase (AST), alkaline phosphatase (ALP), or $>$ ULN total bilirubin ($\geq 1.5 \times$ ULN total bilirubin if known Gilbert's syndrome). If subject has elevations only in total bilirubin that are $>$ ULN and $< 1.5 \times$ ULN, fractionate bilirubin to identify possible undiagnosed Gilbert's syndrome (ie, direct bilirubin $< 35\%$).

For randomized subjects with a baseline result $>$ ULN for ALT, AST, ALP, or total bilirubin, a baseline diagnosis and/or the cause of any clinically meaningful elevation must be understood and recorded in the electronic Case Report form (eCRF).

If subject has $>$ ULN ALT, AST, or ALP that does not meet the exclusion limit at screening, repeat the tests, if possible, prior to dosing to ensure there is no further ongoing clinically relevant increase. In case of a clinically relevant increase, inclusion of the subject must be discussed with the Medical Monitor.

Tests that result in ALT, AST, or ALP up to 25% above the exclusion limit may be repeated once for confirmation. This includes re-screening.

6.3 Withdrawal criteria

Subjects are free to withdraw from the study at any time, without prejudice to their continued care.

Subjects should be withdrawn from the study if any of the following events occur:

1. Subject must be withdrawn if there is an occurrence of status epilepticus, seizure clustering, or generalized tonic-clonic seizure, if unknown for the subject. If seizure frequency is increased, subject can be withdrawn for safety reasons, at the discretion of the Investigator.
2. Subject develops an illness that would interfere with his/her continued participation.
3. Subject is noncompliant with the study procedures or medications in the opinion of the investigator.

4. Subject takes prohibited concomitant medications as defined in this protocol.
5. Parent or legal guardian withdraws his/her consent.
6. The sponsor or a regulatory agency requests withdrawal of the subject.
7. Subject ≥ 6 years of age has active suicidal ideation without specific plan as indicated by a positive response (“Yes”) to question 4 of the “Since Last Visit” version of the C-SSRS. The subject should be referred immediately to a Mental Healthcare Professional and may be withdrawn from the study based upon the investigator’s judgment of benefit/risk of continuing the subject in the study/on study medication.
8. Subject ≥ 6 years of age has active suicidal ideation with a specific plan as indicated by a positive response (“Yes”) to question 5 of the “Since Last Visit” version of the C-SSRS. The subject should be referred immediately to a Mental Healthcare Professional and must be withdrawn from the study.
9. Subject who has cluster seizures prior to Visit 1 intermittently takes benzodiazepines, phenobarbital, or phenytoins more than 1 single administration per week during the study period.
10. Subject on monotherapy needs to add another AED during the First Period.

Investigators should attempt to obtain information on subjects in the case of withdrawal. For subjects considered as lost to follow up, the investigator should make an effort (at least 1 phone call and 1 written message to the subject), and document his/her effort (date and summary of the phone call and copy of the written message in the source documents), to complete the final evaluation. All results of these evaluations and observations, together with a narrative description of the reason(s) for removing the subject, must be recorded in the source documents. The CRF must document the primary reason for withdrawal.

Investigators should contact the Medical Monitor, whenever possible, to discuss the withdrawal of a subject in advance.

6.3.1 Potential drug-induced liver injury IMP discontinuation criteria

Subjects with potential drug-induced liver injury (PDILI) must be assessed to determine if IMP must be discontinued. In addition, all concomitant medications and herbal supplements that are not medically necessary should also be discontinued.

The PDILI criteria below require immediate and permanent discontinuation of IMP:

- Subjects with either of the following:
 - ALT or AST ≥ 5 xULN
 - ALT or AST ≥ 3 xULN and coexisting total bilirubin ≥ 2 xULN

The PDILI criterion below requires immediate discontinuation of IMP:

- Subjects with ALT or AST ≥ 3 xULN who exhibit temporally associated symptoms of hepatitis or hypersensitivity. Hepatitis symptoms include fatigue, nausea, vomiting, right upper quadrant pain or tenderness. Hypersensitivity symptoms include fever (without clear alternative cause), rash, or eosinophilia (ie, $>5\%$).

The PDILI criterion below allows for subjects to continue on IMP at the discretion of the investigator.

- Subjects with ALT or AST $\geq 3 \times \text{ULN}$ (and $\geq 2 \times$ baseline) and $< 5 \times \text{ULN}$, total bilirubin $< 2 \times \text{ULN}$, and no eosinophilia (ie, $\leq 5\%$), with no fever, rash, or symptoms of hepatitis (eg, fatigue, nausea, vomiting, right upper quadrant pain or tenderness).

Evaluation of PDILI must be initiated as described in Section 11.2.1. If subjects are unable to comply with the applicable monitoring schedule, IMP must be discontinued immediately.

Investigators should attempt to obtain information on subjects in the case of IMP discontinuation to complete the final evaluation. Subjects with PDILI should not be withdrawn from the study until investigation and monitoring are complete. All results of these evaluations and observations, as well as the reason(s) for IMP discontinuation and subject withdrawal (if applicable), must be recorded in the source documents. The CRF must document the primary reason for IMP discontinuation.

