11.2.1 Evaluation of PDILI

The PDILI IMP discontinuation criteria for this study are provided in Section 6.3.1, with the accompanying required follow-up investigation and monitoring detailed below. All PDILI events must be reported as an AE and reported to the study site and sponsor within 24 hours of learning of their occurrence. Any PDILI event that meets the criterion for potential Hy's Law must be reported as an AE of special interest (see Section 11.1.1.3), and, if applicable, also reported as an SAE (see Section 11.1.1.2).

Evaluation of PDILI consists of the diagnostic testing and continued monitoring included in Table 11–2 (specific tests dependent on laboratory results and corresponding symptoms) and consultation with a local hepatologist (if applicable; discussed in Section 11.2.1.1). The local hepatologist is the expert usually consulted by the treating physician for assessment and management of potential hepatic disease. This would usually be a hepatologist, but may be a gastroenterologist. Additional investigation and monitoring may be required and adapted based on the diagnosis after the cause of the liver injury/abnormality is confirmed (details in Section 11.2.1.4).

The results of all monitoring, including laboratory testing and other testing, should be made available to the study site and sponsor.

All initial tests resulting in abnormal hepatic laboratory values need to be repeated, but appropriate medical action must not be delayed waiting for the repeat result.

If tests are done locally for more rapid results, a concurrent sample should also be sent to the central laboratory whenever possible. Medical care decisions are to be made initially using the most rapidly available results and a conservative approach must be taken if the results from the 2 laboratory tests are significantly different. Data from the local and central laboratory are to be recorded on the applicable eCRF pages.

When IMP is discontinued, all concomitant medications and herbal supplements that are not medically necessary should also be discontinued. In these cases, the investigator should also consider dose reduction for medically necessary concomitant medication and consider changing any medically required concomitant medication known to be hepatotoxic to a suitable alternative.

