When IMP is stopped due to PDILI (as described in Section 6.3.1), IMP must be permanently discontinued unless a subsequent alternative diagnosis fully explains the hepatic findings. If a subsequent alternative diagnosis fully explains the hepatic findings, and the requirements provided in Section 11.2.1.3 are met, rechallenge with IMP may be appropriate.

Rechallenge with a substance potentially causing drug-induced liver injury is dangerous, may be fatal, and must not occur.

The table below summarizes the approach to investigate PDILI.

This document cannot be used to support any marketing authorization application and any extensions or variations thereof.

Table 11–2: Required investigations and follow up for PDILI

Laboratory value		Symptoms ^a of hepatitis or hypersensitivity	Immediate		Follow up	
ALT or AST	Total bilirubin		Consultation requirements	Actions	Testing	Evaluation
≥3xULN	≥2xULN ^b	NA	Hepatology consult. ^c Medical Monitor must be notified within 24 hours (eg, by laboratory alert) and subject discussed with Medical Monitor ASAP.	Immediate, permanent IMP discontinuation.	Essential: Must have repeat liver chemistry values and additional testing completed ASAP (see Section 11.2.1.3); recommended to occur at the site with HCP.	Monitoring of liver chemistry values at least twice per week until values normalize, stabilize, or return to within baseline values. ^d
≥8xULN	NA	NA		Immediate, temporary or permanent, IMP discontinuation.		
≥3xULN	NA	Yes				
≥3xULN (and ≥2x baseline) and <5xULN	<2xULN	No	Discussion with Medical Monitor required if the criterion that allows for IMP continuation is met.	Further investigation – immediate IMP discontinuation not required (see Section 11.2.1.2).	Not required unless otherwise medically indicated (at discretion of investigator).	

Table 11–2: Required investigations and follow up for PDILI

Laboratory value		Symptoms ^a of hepatitis or hypersensitivity	Immediate		Follow up	
ALT or AST	Total bilirubin		Consultation requirements	Actions	Testing	Evaluation

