≥5xULN (and ≥2x baseline) and <8xULN	<2xULN	No	Hepatology consult if there is no evidence of resolution (see Follow up requirements). ^c Discussion with Medical Monitor required.	IMP discontinuation required if any of the following occur: Subject cannot comply with monitoring schedule. Liver chemistry values continue to increase during 2 week monitoring period. Liver chemistry values remain ≥5xULN (and ≥2x baseline) after 2 week monitoring period.	Essential: Every attempt must be made to have repeat liver chemistry values and additional testing completed within 48 hours at the site with HCP (see Section 11.2.1.3).	Monitoring of liver chemistry values at least twice per week for 2 weeks. ^d Immediate IMP discontinuation required if liver chemistry values continue to increase. After 2 weeks of monitoring liver chemistry values: Discontinue IMP if levels remain ≥5xULN (and ≥2x baseline); monitor until values normalize, stabilize, or return to within baseline values. ^d Continue IMP if levels are no longer ≥5xULN (and ≥2x baseline); continue to monitor at least twice per week until values normalize, stabilize, or return to within baseline values. ^d

ALP=alkaline phosphatase; ALT=alanine aminotransferase; ASAP=as soon as possible; AST=aspartate aminotransferase; HCP=healthcare practitioner;

IMP=investigational medicinal product; NA=not applicable; PDILI=potential drug-induced liver injury; ULN=upper limit of normal

^a Hepatitis symptoms include fatigue, nausea, vomiting, and right upper quadrant pain or tenderness; hypersensitivity symptoms include eosinophilia (>5%), rash, and fever (without clear alternative cause).

^b If the subject also has ≥2xULN ALP, the possibility of an indication of biliary obstruction should be discussed with the Medical Monitor.

^c Details provided in Section 11.2.1.1. The local hepatologist is the expert usually consulted by the treating physician for assessment and management of potential hepatic disease. This would usually be a hepatologist, but may be a gastroenterologist.

^d Unless an alternative monitoring schedule is agreed by the investigator and UCB responsible physician. Determination of stabilization is at the discretion of the investigator in consultation with the hepatologist (as applicable) and UCB responsible physician, as needed.

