11.2.1.1 Consultation with Medical Monitor and local hepatologist

Potential drug-induced liver injury events require notification of the Medical Monitor within 24 hours (eg, by laboratory alert), and the subject must be discussed with the Medical Monitor as soon as possible. If required, the subject must also be discussed with the local hepatologist. The local hepatologist is the expert usually consulted by the treating physician for assessment and management of potential hepatic disease. This would usually be a hepatologist, but may be a gastroenterologist. If determined necessary, this discussion should be followed by a full hepatology assessment (see Section 11.2.1.3) and SAE report (if applicable).

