11.2.1.2 Immediate action: determination of IMP discontinuation

All PDILI events require immediate action, testing, and monitoring.

The immediate action is dependent on the laboratory values and symptoms of hepatitis or hypersensitivity and ranges from continuation of IMP (followed by immediate investigation) to immediate and permanent discontinuation (see Section 6.3.1 and Table 11-2 for details).

When IMP is discontinued, all concomitant medications and herbal supplements that are not medically necessary should also be discontinued. The investigator should also consider dose reduction for medically necessary concomitant medication and consider changing any medically required concomitant medication known to be hepatotoxic to a suitable alternative.

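### Protocol 6.3.1 and Table 11-2 prescribe incompatible actions for asymptomatic ALT/AST from 5x to below 8xULN: stop the drug at once, or continue under monitoring

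*Protocol*

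**What the plan says.** Protocol 6.3.1 sorts potential drug-induced liver injury (PDILI) results by required action. Its first group opens with "The PDILI criteria below require immediate and permanent discontinuation of IMP" and contains two entries: ALT or AST at or above 5xULN, and ALT or AST at or above 3xULN with total bilirubin at or above 2xULN. The first entry carries no upper limit and no condition on symptoms, bilirubin or baseline multiple. The only group that leaves continuation to the investigator covers 3x to below 5xULN (at least twice baseline), with bilirubin below 2xULN and no symptoms.

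Table 11-2 in Protocol 11.2.1 has a separate row for 5x to below 8xULN with at least twice baseline, bilirubin below 2xULN and no symptoms. Its Actions cell begins "IMP discontinuation required if any of the following occur: Subject cannot comply with monitoring schedule" and adds two further triggers: values that go on rising during the 2-week monitoring period, and values still at or above 5xULN (and twice baseline) when it ends. Its Evaluation cell then says "Continue IMP if levels are no longer ≥5xULN (and ≥2x baseline"). SAP 12.3.3 repeats the row.

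The linking text is as follows.
- Section 11.2.1 opens with "The PDILI IMP discontinuation criteria for this study are provided in Section 6.3.1, with the accompanying required follow-up investigation and monitoring detailed below".
- It later says "When IMP is stopped due to PDILI (as described in Section 6.3.1), IMP must be permanently discontinued unless a subsequent alternative diagnosis fully explains" (that is, accounts for) what was seen in the liver, in which case rechallenge may be considered.
- It introduces the table with "The table below summarizes the approach to investigate PDILI".
- Section 11.2.1.2 says that the immediate action ranges from continuing the drug "to immediate and permanent discontinuation (see Section 6.3.1 and Table 11-2 for details").

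**The concern.** For one laboratory profile an investigator finds two instructions that cannot both be followed. This is a hepatic stopping rule in children from 1 month of age, so an error either way has a cost. Following the table can leave a child on drug that 6.3.1 says to stop. Following 6.3.1 can permanently remove an antiepileptic drug when the table would have allowed it to continue under close monitoring. It is also unclear whether a site that follows the table has committed a protocol deviation.

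**Working it through.** No figure in the plan needs reproducing. The check is to take one profile through both texts: ALT or AST from 5x to below 8xULN, at least twice baseline, bilirubin below 2xULN, no symptoms of hepatitis or hypersensitivity.

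| Question | Protocol 6.3.1 | Table 11-2 (and SAP 12.3.3) |
|---|---|---|
| Does the profile fall under a listed criterion? | Yes: at or above 5xULN, unbounded | Yes: its own row |
| Action on day 0 | Stop | Stay on drug and monitor, if the schedule can be followed |
| Is continuation possible? | No: that group ends below 5xULN | Yes, if values fall |
| When is a stop required? | Day 0 | On failure to monitor, on continued rise, or at 2 weeks if still at or above 5xULN and twice baseline |
| Is the stop permanent? | Yes, subject to the alternative-diagnosis exception in 11.2.1 | Not stated in the row |

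**Time on drug.** Under 6.3.1 the required stop is at day 0. Under the table the latest required stop for a value that stays high is 2 weeks x 7 = 14 days. Within that time there are at least 2 tests per week x 2 weeks = 4 liver tests, unless another schedule is agreed. If values fall below the limit, the table requires no stop. The difference is therefore 0 days against up to 14 days, or no stop.

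**How much of the band the row covers.** Exclusion criterion 18 bars ALT or AST at or above 3xULN at entry. A value of 5xULN is at least twice baseline whenever baseline is at most 5 / 2 = 2.5xULN. So at 5xULN the twice-baseline condition removes only children who entered between 2.5x and 3xULN. At 6xULN or above it removes nobody who met the criterion (6 / 3 = 2). That condition barely narrows the conflict.

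**Is it a slip in one cell?** No. The row says the same thing in its Actions and Evaluation columns and appears again in the SAP. The amendment summaries record no change to 6.3.1 or Table 11-2, so both are current text.

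**The case against.** The best defence is that 6.3.1 already governs. Section 11.2.1 names it as the home of the stopping criteria and refers back to it when describing a stop, and the table is introduced as a way to investigate. That evidence is good, and it is the reason to correct the table rather than 6.3.1. It does not remove the conflict: the table has its own Actions column, the disputed row expressly continues the drug, and 11.2.1.2 cites both places for the immediate action.

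A second defence is oversight. Section 11.2.1.1 states "Potential drug-induced liver injury events require notification of the Medical Monitor within 24 hours", and the disputed row itself requires discussion with the Medical Monitor. This makes divergent handling less likely, but the Medical Monitor reads the same two texts. The entry limit of 3xULN also bounds exposure to the problem, and the documents give no expected frequency for this range.

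A reader might go further and infer that the 6.3.1 stop could mean longer exposure than the table. Section 7.2 says, under its First Period heading, that down-titration applies on early discontinuation. From the top dose that is two 2-week steps, or 28 days, against the 14-day monitoring window. The comparison does not hold, because it applies the taper to one side only. If a taper followed a table stop at day 14, the total would be 14 + 28 = 42 days. Like for like it is 0 against up to 14 days without a taper, or 28 against up to 42 days with one. The 6.3.1 route is shorter in both. The ordinary reading is in any case that a specific immediate safety stop overrides a general taper rule.

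**Conclusion.** The inconsistency is real and should be fixed. For asymptomatic ALT or AST from 5x to below 8xULN (at least twice baseline, bilirubin below 2xULN), the required stop is at day 0 under 6.3.1. Under Table 11-2 it is up to 14 days later, or never if values fall. This assumes the table's default monitoring schedule and no taper on either side.

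Three limits apply. The documents are not silent on which text leads, since 11.2.1 points to 6.3.1. The word permanent is qualified by the alternative-diagnosis exception. The SAP copy supports reporting and does not direct treatment. A reader might also infer an effect on the efficacy result, but nothing here enters the primary analysis. How many of the 38 planned primary-analysis and 10 planned monotherapy subjects would meet this range cannot be derived from the documents.

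**What to change.** By protocol amendment:
- In Table 11-2 and SAP 12.3.3, delete the row for 5x to below 8xULN. Change the 8xULN stop row to 5xULN with immediate, permanent discontinuation.
- Alternatively, if the clinical team documents a reason to prefer 8xULN, amend 6.3.1 so that both places state that one rule.
- In either case, confirm whether the ALT above 8xULN condition for prothrombin time/INR in Protocol Table 11-3 and SAP 12.3.4 should stay.

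Two optional clarifications can go in at the same time. One sentence could say that the general down-titration rule does not delay an immediate PDILI stop. The SAP 10.3.3 listing cut-offs (strictly greater than) could be matched to the SAP 10.3.2 table (greater than or equal to); this affects only values exactly at a limit.

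The cost is an amendment under Protocol 14.5, with sponsor, IRB/IEC and, where required, regulatory approval, plus matching SAP text. It adds no assessments and no data collection.
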